3.3 Inclusion of Women and Minorities

Men and women as well as members of all races and ethnic groups are eligible for this trial.

4 REGISTRATION PROCEDURES

Subject must not start any protocol intervention prior to registration through the Siteman Cancer Center. The subject must read, understand and sign the Institutional Review Board approved consent form. The following steps must be taken before registering subjects to this study:

1. Confirmation of patient eligibility
2. Registration of patient in the Siteman Cancer Center OnCore database

3. Assignment of unique patient number (UPN)

4.1 Confirmation of Patient Eligibility

All necessary procedures and evaluations must be performed to document that the subject meets all of the inclusion criteria and none of the exclusion criteria prior to first dose on Day 1. Adult subjects must read, understand, and sign the Institutional Review Board/Research Ethics Board/Independent Ethics Committee (IRB/REB/IEC) approved informed consent form (ICF) confirming his or her willingness to participate in this study before any study-specific screening procedures are performed. Subjects less than 18 years of age will not be enrolled on this study. Subjects must also grant permission to use protected health information per the Health Insurance Portability and Accountability Act (HIPAA).

Confirm patient eligibility by collecting the information listed below:

1. Registering MD's name
2. Patient's race, sex, and DOB
3. Three letters (or two letters and a dash) for the patient's initials
4. Copy of signed informed consent form
5. Completed eligibility checklist, signed and dated by a member of the study team
6. Copy of appropriate source documentation confirming patient eligibility

4.2 Patient Registration in the Siteman Cancer Center OnCore Database

All subjects must be registered through the Siteman Cancer Center OnCore database.

4.3 Assignment of UPN

Each patient will be identified with a UPN for this study. All data will be recorded with this identification number on the appropriate CRFs.

5 TREATMENT OF SUBJECTS AND STUDY DESIGN

This is a single center, open-label pilot and feasibility study of prophylactic belimumab for the prevention of chronic GvHD following alloHCT at Washington University School of Medicine in St. Louis. The study will include Screening Phase, Treatment Phase, and Follow-up Phase.

Subjects will be screened for the study after obtaining the results from their standard-of-care Day +30 bone marrow biopsy. Those subjects meeting the Inclusion and Exclusion Criteria will be enrolled in the study and start treatment between Day +30 and Day +80 after alloHCT. At enrollment, subjects may continue on steroids that were used to treat acute GvHD. At the time of enrollment, however, subjects should be responding to therapy and the dose of steroid should be ≤ 0.5 mg/kg/day of prednisone equivalent with no dose increase in the preceding 1 week. Subjects may also remain on other systemic immunosuppressive drugs that were used to prevent or treat acute GvHD. At the time of enrollment, acute GvHD should be grade II or less. Subjects diagnosed with or treated for chronic GvHD will be excluded from the study. The study population will include 10 subjects. Planned duration of treatment is for 7 cycles (6 months; see study schema). Subjects will be followed for 24 months. One of the secondary endpoints is to evaluate the impact of

belimumab on incidence and severity of chronic GvHD. The subjects who develop chronic GvHD while receiving treatment with the study drug, belimumab, may continue on the study at the discretion of treating transplant physician with careful documentation of their GvHD severity and treatments used for it. If at any point it is considered that the study drug may be contributing to chronic GvHD it will be discontinued.

The primary endpoint is safety and tolerability of belimumab. Subjects who receive at least one dose of belimumab will be eligible for primary endpoint analysis and it will be performed according to the CTCAE v4.03.

Diagnosis of chronic GvHD will be per NIH criteria (**Appendix B**). Those patients diagnosed with chronic GvHD will have organ specific staging and global scoring according to the NIH criteria (**Appendices D and E**).

5.1 Baseline Evaluations

5.1.1 Medical History and Demographics

The subject's relevant medical history through review of medical records and by interview will be collected and recorded. Concurrent medical signs and symptoms must be documented to establish baseline severities. A disease history and the date of initial diagnosis will be recorded.

5.1.2 Prior and Concomitant Medications

All active medications from 30 days prior to signing of ICF through 30 days after the last dose of study drug will be documented. All prior and current treatments for acute and chronic GvHD will be documented.

5.1.3 History and physical neurological, and psychiatric exam, vital signs and ECOG performance score

The physical examination will include the general appearance of the subject, height (Screening only) and weight, and examination of the skin, eyes, ears, nose, throat, lungs, heart, abdomen, extremities, musculoskeletal system, nervous system, and lymphatic system. Vital signs will include blood pressure, heart rate, respiratory rate, and body temperature. ECOG performance score will be recorded (Appendix C).

5.1.4 Laboratory

5.1.4.1 Bone Marrow Biopsy

Remission will be assessed as defined in the Inclusion Criteria. It will be evaluated using a local laboratory and include pathology review, minimal residual disease and engraftment testing.

5.1.4.2 Hematology

Hematology will be evaluated using a local laboratory and parameters will include a complete blood count: white blood cells, red blood cells, hemoglobin, hematocrit, platelets, neutrophils, lymphocytes, monocytes, eosinophils, basophils.

5.1.4.3 Chemistry

Serum chemistry will be evaluated using a local laboratory and parameters will include sodium, potassium, chloride, blood urea nitrogen (BUN)/Urea, creatinine, glucose, calcium, total protein, albumin, AST, ALT, alkaline phosphatase, total bilirubin, LDH, phosphate, uric acid, magnesium and bicarbonate.

5.1.4.4 Hepatitis Serologies

Hepatitis serologies will be evaluated using a local laboratory and include hepatitis C antibody, hepatitis B surface antigen, and hepatitis B core antibody. If hepatitis B core antibody, hepatitis B surface antigen, or hepatitis C antibody is positive, then PCR to quantitate hepatitis B DNA or hepatitis C RNA must be performed.

5.1.4.5 Serum Immunoglobulins

Serum immunoglobulins will be evaluated using a local laboratory and include IgA, IgG and IgM levels.

5.1.4.6 Pregnancy test

Serum pregnancy test is required at Screening using a local laboratory and only for women of childbearing potential.

5.1.5 ECG

At Screening, 12-lead ECG is required and will be done in triplicate (≥ 1 minute apart). Any clinically significant abnormalities noted at Screening should be included in the medical history.

ECGs should be performed at the investigator's discretion, particularly in subjects with arrhythmic symptoms (e.g. palpitations, lightheadedness) or new onset of dyspnea.

5.1.6 Chronic GvHD Assessment

Patients should be assessed for chronic GvHD and no active chronic GvHD should be present. Please see Diagnostic Criteria for Chronic GvHD (Appendix B).

5.1.7 Correlative pharmacodynamics and immunology studies

Refer to Section 9.0.

5.2 Study Drug Administration

Belimumab will be administered intravenously at 10 mg/kg over 1 hour. Enrollment and the first dose of belimumab (Cycle 1) will be administered between Day +30 and Day +80 after alloHCT, after reviewing bone marrow biopsy results and confirming eligibility. Subjects will receive belimumab every 2 weeks for 3 cycles and then every 4 weeks for a total of 7 cycles (6 months of therapy).

Therefore: Cycle 1 of belimumab will be administered between Day +30 and +60 after alloHCT, Cycle 2 will be administered 2 weeks later (+/- 3 days), Cycle 3 will be administered two weeks after Cycle 2 (+/- 3 days), and each subsequent cycle will be given every 4 weeks thereafter (+/- 1 week) for total of 7 cycles (6 months of therapy). This dosing and schedule of belimumab administration is similar to prior phase III studies for systemic lupus erythematosus [38, 39]. Subjects will continue to adjust their standard of care immunosuppressive medications at the discretion of treating physician.

5.3 Premedication

Premedication with an oral antihistamine, with or without an antipyretic, may be administered before the infusion of belimumab.

5.4 Duration of Therapy

Treatment may continue for six months, or until one of the following criteria applies:

- Documented and confirmed original hematologic disease relapse
- Death
- Adverse event(s) that, in the judgment of the investigator, may cause severe or permanent harm or which rule out continuation of study drug
- General or specific changes in the patient's condition render the patient unable to receive further treatment in the judgment of the investigator
- Grade III-IV acute GvHD not responding to therapy after 2 weeks
- Serious noncompliance with the study protocol
- Lost to follow-up
- Patient withdraws consent
- Investigator removes the patient from study
- The Siteman Cancer Center decides to close the study

If at any time the constraints of this protocol are considered to be detrimental to the patient's health and/or the patient no longer wishes to continue protocol therapy, the protocol therapy should be discontinued and the reason(s) for discontinuation documented in the case report forms. Subjects who prematurely discontinue treatment for any reason will be followed as indicated in the study calendar.

5.5 Duration of Follow-up

Subjects will be followed after discontinuation of treatment every 3 months during the first 2 years post-C1D1 and then annually for 5 years post-C1D1 or until death, whichever occurs first. Subjects removed from study for unacceptable adverse events will be followed until resolution or stabilization of the adverse event.

5.6 Concomitant Medication and Supportive Care Guidelines

5.6.1 Permitted Concomitant Medications

All systemic immunosuppressive medications with exact doses and additional treatment modalities for chronic GvHD will be recorded at time of every visit. Adjustment to immunosuppressive medications or initiation of additional treatment modalities for treatment of chronic GvHD will be at the discretion of the treating transplant oncologist. Systemic immune suppressive medications that the patient is already receiving at the time of enrollment will be tapered at the discretion of the treating transplant oncologist.

Infectious prophylaxis should follow institutional guidelines. All patients should continue on prophylaxis against viral, fungal and pneumocystis infections.

5.6.2 Prohibited Medications

After prior B-cell therapy, there must be a wash-out of 5 therapeutic half-lives, when pharmacodynamic effect would be minimal (e.g., one year following rituximab).

From the time of initiation of conditioning regimen subjects must not have received any biologic investigational agent (i.e. any drug not approved for sale in the country in which it is being used).

For 30 days prior to administration of belimumab (or 5 half-lives, whichever is greater) subjects must not have received any non-biologic investigational agent (i.e. any drug not approved for sale in the country in which it is being used).

Live vaccines should not be given within 30 days prior to administration of belimumab or concurrently with belimumab.

5.6.3 Supportive Care Guidelines

Supportive medications in accordance with standard practice (such as for emesis, diarrhea, etc.) are permitted. Use of neutrophil growth factors and red blood cell growth factors is permitted per institutional policy and in accordance with the ASCO guidelines. Transfusions may be given in accordance with institutional policy.

5.7 Management of Adverse Clinical Events and Dose Modification Guidelines

Belimumab is generally a well-tolerated agent. Most common adverse reactions are: nausea, diarrhea, pyrexia, nasopharyngitis, bronchitis, insomnia, depression, migraine. Management guidelines for some potential events are outlined below. Further details are available in the Investigator's Brochure. All serious AEs, including AEs of Special Interest, i.e., serious hypersensitivity or infusion reactions; serious infections, including herpes zoster and opportunistic infections; malignancy; and/or Suicidal thought, intent or behaviour must be reported to GSK within 24 hours of awareness.

Hypersensitivity and Infusion Reactions

Site personnel will be aware of the risk of hypersensitivity reactions, which may present as infusion reactions, and monitor subjects closely. Subjects should remain under clinical supervision for 3 hours after completion of the first 2 infusions. The infusion rate may be slowed or interrupted if the patient develops an infusion reaction. Should symptoms of acute hypersensitivity occur, an extended period of monitoring may be appropriate based on clinical judgment. This may include, but is not limited to, monitoring vital signs and observing any untoward reactions. Beyond the first 2 infusions, subjects should be monitored during infusion and for 30 minutes after infusion according to standard operating procedure for IV infusions. Infusion reactions occurred more frequently on the first two infusion days and tended to decrease with subsequent infusions. Delay in the onset of acute hypersensitivity reactions has been observed with recurrence of clinically significant reactions after initial resolution of symptoms following appropriate treatment. Therefore, subjects should be monitored during and for an appropriate period of time after administration of belimumab. Delayed-type, non-acute hypersensitivity reactions have also been observed and included symptoms such as rash, nausea, fatigue, myalgia, headache, and facial edema.

Serious infections

Serious infections, including herpes zoster and opportunistic infections are rare, but possible. Infection prophylaxis should follow institutional guidelines. If patient develops infection requiring intravenous or intramuscular antibiotics, belimumab may be held for up to two weeks and will then be administered. If a patient needs a dose held for more than two weeks, the PI will be contacted to determine suitability for further study participation.

Rash with or without pruritus

Rash should be managed symptomatically according to standard medical practice. Patient should be evaluated for presence of acute GvHD (see guidelines below).

Elevation of liver enzymes

Elevation of liver enzymes is not listed as an expected adverse event with belimumab. However, elevated liver enzymes can occur in the context of acute GvHD and such patients should be evaluated for presence of acute GvHD.

Nausea and/or vomiting

Standard anti-emetics may be used for prophylaxis and treatment of nausea or vomiting.

Diarrhea

Diarrhea should be managed according to clinical practice. Patient should be evaluated for presence of acute GvHD (see guidelines below).

Depression and suicidality

Some autoimmune diseases have an increased risk of depression and suicidal behavior and/or ideation [Bachen, 2009; Timonen, 2003; Stenager, 1992]. For this reason, in studies of subjects with autoimmune disease, subjects should be assessed for depression, suicidal ideation and/or behavior at each visit by the treating physician (to be recorded in a physician note).

Progressive Multifocal Leukoencephalopathy (PML)

PML resulting in neurological deficits, including fatal cases, has been reported in SLE subjects receiving immunosuppressant pharmacotherapy, including belimumab. A

diagnosis of PML should be considered in any subject presenting with new-onset or deteriorating neurological signs and symptoms. The subject should be referred to a neurologist or other appropriate specialist for evaluation. If PML is confirmed, belimumab should be discontinued and consideration should be given to stopping immunosuppressant therapy.

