5.8 Acute GvHD

Any patient with new rash, diarrhea or elevated liver enzymes should be evaluated for presence of acute GvHD. In the event a study participant were to develop acute GvHD grade III-IV after initiating belimumab therapy, belimumab treatment will be held. Belimumab administration can be delayed for up to two weeks, however, if the grade of acute GvHD does not improve to grade II or less by that time, belimumab will be discontinued indefinitely and patient will be taken off study.

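### Section 5.7 makes the belimumab hold optional for an infection needing IV or IM antibiotics and does not require that the infection be controlled before re-dosing

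*Combined protocol and SAP*

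**What the plan says.** Section 5.7, under serious infections, sets the rule: "If patient develops infection requiring intravenous or intramuscular antibiotics, belimumab may be held for up to two weeks and will then be administered". The next sentence deals with longer holds: "If a patient needs a dose held for more than two weeks, the PI will be contacted to determine suitability for further study participation". The section opens by describing its own status, "Management guidelines for some potential events are outlined below", and refers to the Investigator's Brochure for more detail.

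Two other events are handled by condition:

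- Confirmed PML, also in 5.7: "If PML is confirmed, belimumab should be discontinued and consideration should be given to stopping immunosuppressant therapy".
- Severe acute GvHD, in 5.8: "In the event a study participant were to develop acute GvHD grade III-IV after initiating belimumab therapy, belimumab treatment will be held", and after a delay of at most two weeks, "if the grade of acute GvHD does not improve to grade II or less by that time, belimumab will be discontinued indefinitely".

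Section 5.4 adds general reasons to stop treatment. One is "Adverse event(s) that, in the judgment of the investigator, may cause severe or permanent harm or which rule out continuation of study drug". Another applies when changes in the patient's "condition render the patient unable to receive further treatment in the judgment of the investigator". The same section says that therapy should stop if the protocol's constraints are thought harmful to the patient.

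**The concern.** Subjects start belimumab 30 to 80 days after an allogeneic transplant. They may still be on steroids and other immunosuppressants (Section 5), and they then receive a drug that reduces B-cell survival. Section 1.2.3 reports no observed rise in serious infections in lupus, but says the mechanism could raise that risk. Section 7.1.4.1 lists serious infection as an event of special interest, and safety is the primary endpoint.

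An infection that needs parenteral treatment is thus one of the events for which a clear dosing rule matters most. The rule in 5.7 has a permissive verb for the hold, a time limit for its length and a directive verb for the next dose. It does not mention the state of the infection. At stake is whether avoiding a dose during an uncontrolled infection is a step the protocol requires, or depends on someone choosing to invoke a general clause.

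**Working it through.** The point rests on wording, so the check is a comparison of rules. The plan states no figure for it.

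**Rules side by side**

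| Event | Is the hold required? | What allows the next dose? | What if it has not improved at two weeks? |
|---|---|---|---|
| Infection needing IV/IM antibiotics (5.7) | No, optional | Nothing about the infection; dosing follows a hold of at most two weeks | PI contacted only if a longer hold is needed; no criterion given |
| Grade III-IV acute GvHD (5.8) | Yes | Improvement to grade II or less | Permanent discontinuation |
| Suspected pregnancy (5.9) | Yes, immediate stop | Confirmation that the patient is not pregnant | Not applicable |
| Confirmed PML (5.7) | Drug should be discontinued | Not applicable | Not applicable |

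**Does anything else supply the missing condition?**

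1. *PI contact (5.7).* This is triggered only when a hold beyond two weeks is needed. A subject dosed on schedule, or at the end of a 14-day hold, never reaches it.
2. *Stopping clauses (5.4).* They allow treatment to stop on the investigator's judgment. They are not specific to infection and are not tied to a check before each dose.
3. *Dose-visit assessments (10.1).* History and physical, vital signs, blood count and chemistry are scheduled at every cycle. They provide the information, but no rule says what to do with it.
4. *Ongoing monitoring of serious toxicity (Section 11).* This is oversight, with no pre-dose condition.
5. *Entry criteria 9 and 10 (3.2).* Active infection and recent parenteral anti-infectives are barred before the first dose only.

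None of the five requires a hold, and none sets a condition on the infection before a later dose.

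**Scale only.** The calendar puts C1 to C7 at weeks 0, 2, 4, 8, 12, 16 and 20. The gaps are 14, 14, 28, 28, 28 and 28 days, 140 days in total. Assume onset is equally likely on each of the 140 days and a parenteral course lasts L days. The share of onset dates for which the next dose falls inside the course is:

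- No hold: Σ min(gap, L) / 140. For L = 7, 14, 21 and 42 this is 42/140 = 30%, 84/140 = 60%, 112/140 = 80% and 140/140 = 100%.
- Full 14-day hold: Σ min(gap, max(L − 14, 0)) / 140. This is 0%, 0%, 42/140 = 30% and 140/140 = 100%.

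Onset pattern and course length are my assumptions; the documents give neither. The percentages describe overlap with antibiotic treatment. A patient can be on antibiotics with the infection well controlled, so they do not measure the defect and the point does not depend on them.

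**Section 13.** Its two probability statements for n = 10 hold up: 1 − 0.80^10 = 0.893 against the stated 90%, and 1 − 0.95^10 − 10 × 0.05 × 0.95^9 = 0.086 against the stated upper limit of 10%. Neither depends on the hold rule.

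**The case against.** The strongest reply is that 5.7 is a workable two-tier rule. Two weeks is a ceiling, not a timer: the treating physician may hold up to that point, and a longer hold goes to the PI. Someone must judge need by then, with a clinical examination at every dose visit in a single-centre study of 10 subjects. This largely stands as a description of likely practice. It is why the point cannot be stated more strongly.

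A reader might infer that 5.7 compels a dose at two weeks whatever the patient's state. The documents do not support that: the PI-contact sentence and 5.4 both allow the dose to be withheld. A reader might also see a conflict with the entry criteria on infection. There is none, because those criteria apply before the first dose.

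Other objections carry some weight:

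- *Acute GvHD has a grading scale (Appendix F) and infections share none.* True, so a numerical threshold cannot simply be copied from 5.8. A required hold and a documented judgment need no scale.
- *PML is a permanent stop, not a hold-and-resume rule.* Also true. It shows only that 5.7 can tie dosing to a condition.
- *A two-week hold changes exposure only modestly.* With the terminal half-life of 19.4 days in Section 1.2.4, about 0.5^(14/19.4) = 61% of the drug present remains after 14 days. The documents do not show how far a hold lowers risk. The same slow elimination means that a dose given at the wrong time cannot be quickly undone.
- *Serious infections are reported to the manufacturer within 24 hours, and a possibly related death suspends the study (5.10).* Both act after the event.
- *The Investigator's Brochure may hold a criterion.* It is not available here, so this cannot be settled. If it does, 5.7 should restate it.

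**Conclusion.** The point holds as a cheap patient-safety improvement that should be made. For infections needing IV or IM antibiotics, 5.7 permits a dose while the infection is uncontrolled, and no required pre-dose step prevents it. It does not force such a dose.

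The reach is six of seven doses in each of 10 subjects. How many would be affected cannot be estimated from the documents. Reading the overlap percentages as a count of subjects harmed, or as what the fix would prevent, would be wrong: they rest on assumed onset and course length, they ignore the judgment clauses, and they count controlled infections too. The sample size, the confidence interval and the safety probabilities are unaffected.

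The conclusion rests on the protocol text alone. The documents do not state accrual status; if dosing is complete, the change benefits only a successor protocol.

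**What to change.** Replace the hold and PI-contact sentences in the serious-infections paragraph of 5.7 with wording such as:

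> For any infection that needs IV or IM antibiotics, belimumab will be held. Dosing resumes only once the investigator documents that the infection is controlled. If control is not reached within two weeks, the PI is contacted and decides whether the hold continues or belimumab is stopped; no dose is given while the infection is uncontrolled.

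This still relies on clinical judgment. It differs from the present text in that holding is the default, the judgment is a recorded step before the dose, and the PI's options do not include dosing through an uncontrolled infection.

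The cost is one protocol paragraph, with no added visits or subjects. Some doses may be delayed or missed. A subject infected between C1 and C2 who never resumes would fall short of the two cycles that 8.2 requires for secondary endpoints. Under uniform onset, that interval is 14/140 = 10% of the at-risk days. Such a subject would stay in the safety analysis under 8.1.
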